5.1.2 Per-Protocol

The Per-Protocol (PP) population is defined as a subset of the FAS population who completed the treatment originally allocated (i.e., always received the assigned treatment (vosoritide or placebo)), with a standing height/body length assessment at Week 52 following protocol window, and with treatment compliance of at least 80%.

The PP population will be used for sensitivity analysis of the primary and key secondary efficacy endpoints only.

5.1.3 Safety

The Safety Population is a subset of the FAS who receive at least one dose of vosoritide or placebo in the study. The Safety Population will be used to present the safety summaries by actual treatment received. Subjects randomized to one treatment group, who only receive the study treatment for the other treatment group, will be analyzed in the arm of the study treatment they received.

The Safety Population will be used to present the safety data.

5.1.4 PK

The PK Population is defined as all sentinel subjects and subjects randomized to vosoritide treatment group, who received at least one dose of vosoritide in this study and have at least one evaluable PK concentration.

5.1.5 Immunogenicity

The Immunogenicity Population is defined as all subjects in the Safety Population who have at least one evaluable immunogenicity sample. Subjects randomized to one treatment group, who only receive the study treatment for the other treatment group, will be analyzed in the arm of the study treatment they received.

5.2 Pooling of Data from Sites with Small Enrollment

Not applicable, as there are no analyses by site.

5.3 Study Day Derivation

Study day in 111-206 will be determined by subtracting the initial study treatment start date from a visit date plus 1 if the visit date occurs on or after the initial study treatment start date. Otherwise, the study day will be the visit date minus the initial study treatment start date. Therefore, Study Day 1 will occur on the initial study treatment start date. i.e.

- Study Day 1 = Day of first dose of study treatment.
- If Visit Date < Study Treatment Start Date, then Study Day = Visit Date - Study Treatment Start Date
- If Visit Date >= Study Treatment Start Date, then Study Day = Visit Date - Study Treatment Start Date +1

5.4 Visit Windows for Analysis

An assessment for a subject will be classified according to the study day of the assessment where it falls within a window.

Observational data in 111-901 for subjects who enrolled in 111-206 and are included in the corresponding analysis population will be used in efficacy summary tables and figures. For Cohort 3 subjects, data from the observational period in 111-901 or 111-206 will be included. The analysis visits and windows for observational assessments in 111-901 and 111-206 are defined in [Table 5.4.1](#). Unless otherwise specified, only the derived visits listed in the table will be included in summary tables and figures.

Table 5.4.1: Visit Windows for Observed Assessments in BMN 111-901 and BMN 111-206

Derived Visit	Target Day ^a	Analysis Window ^a
3 Months Prior in 111-206 or 111-901 for Cohort 3 subjects*	-91	target day +/- 42 days
6 Months Prior in 111-901*	-182	target day +/- 42 days

^a Target days and analysis windows are relative to the 111-206 Day 1 date defined in Section 5.3 above.

* In the event a subject does not have an assessment in the 3 months prior or 6 months prior window then the closest assessment to the target date will be considered. If the two closest assessments to the target day are equidistant from the target day, the latest assessment will be used.

For each subject and growth measure in study 111-901, the record closest to the target day within the analysis window will be retained for inclusion in summary tables.

Spaghetti plots of standing height/body length Z-Score will include measures every 6 months recorded and including the “6 months prior”, “3 months prior” for subjects in Cohort 3 from Study 111-901 or 111-206. This will allow for all subjects with height assessments 3 months prior to Day 1 to have at least one assessment included.

The analysis windows for assessments in 111-206 are defined in Table 5.4.2. The analysis windows are designated to be consecutive for scheduled visits to accommodate delayed visits due to impact of COVID-19. The upper bound of each visit window will be target day plus half of the difference between the current target day and the next target day, and the lower bounds of the window will be the upper bound of the previous window plus 1 except for Day 1, Day 2, Day 3, and Week 52. Lower bound, upper bound, and target date are the same for Day 1, Day 2, and Day 3. The upper bound of Week 52 will be target day plus 42 days. If there are two or more assessments within a designated window, the assessment that is closest to the target day will be used for analyses. If the two closest assessments to the target day are equidistant from the target day, the assessments taken on a scheduled visit per case report form (CRF) page will be used; if both are scheduled visits but not on the same day, the latest assessments will be used; if both are on the same day, the average of the assessments will be used. Unless otherwise specified, all analyses are based on derived visits.

Table 5.4.2: Visit Windows for Observed Assessments in 111-206

Derived Visit	Target Day ^a	Analysis Window ^a
Baseline		The last assessment prior to the first dose of study treatment unless otherwise specified.
Day 1	Day 1	Day 1
Day 2	Day 2	Day 2
Day 3	Day 3	Day 3
Day 8	Day 8	Day 4 - 15
Week 3	Day 22	Day 16 - 33
Week 6	Day 43	Day 34 - 68
Week 13	Day 92	Day 69 - 117
Week 20	Day 141	Day 118 - 162
Week 26	Day 183	Day 163 - 229
Week 39	Day 274	Day 230 - 320
Week 52	Day 365	Day 321 - 407

^a Target days and analysis windows are relative to Day 1 date defined in Section 5.3.

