17 BONE METABOLISM BIOMARKERS

Bone metabolism biomarkers (both blood and urine) will be collected to assess changes in bone metabolism. The safety population will be used for all summaries.

Serum samples for bone metabolism blood biomarkers (collagen X and bone-specific alkaline phosphatase [BSAP]) are collected pre-dose at baseline, Day 8, Week 6, Week 20, Week 39, early termination visit. Urine samples for bone metabolism urine biomarkers (Cross-linked C-Telopeptide of Collagen Type II [CTX-II]) are collected pre-dose on Day 1, Day 2, Day 3, Week 3, Week 13, Week 26, Week 39, Week 52, and early termination visit.

For BSAP and Collagen X, the absolute values, and change from baseline at scheduled visits will be summarized separately by cohort and overall by treatment group using format as specified in [Table 5.4](#).

For CTX-II, the absolute values normalized by creatinine, and change from baseline at scheduled visits will be summarized separately by cohort and overall by treatment group using format as specified in [Table 5.4](#).

A box plot of change from baseline in BSAP, Collagen X, CTX-II normalized by urine creatinine over time will be provided for pooled sentinel subjects and randomized subjects received active treatment.

Bone metabolism biomarkers will be listed by cohort, sentinel/randomized subjects, treatment group, subject ID, and visit.

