19 IMMUNOGENICITY ASSESSMENT

Serum samples for anti-drug antibody (ADA) testing will be drawn pre-dose on Day 1, Week 3, Week 13, Week 26, Week 52, and early termination visit. Blood (serum) samples for testing drug-specific IgE will be drawn on Day 1 and in the event of a Grade 3 or significant hypersensitivity adverse event, or at the investigator's discretion.

ADA testing will include anti-vosoritide total antibody (TAb); TAb cross-reactive with endogenous C-type natriuretic peptide (CNP), brain natriuretic peptide (BNP) or atrial natriuretic peptide (ANP); and anti-vosoritide neutralizing antibody (NAb).

NAb testing and TAb testing for cross-reactivity with endogenous CNP, ANP or BNP will be performed only on baseline and TAb positive samples. NAb testing will not be performed if the corresponding TAb is negative. A listing for each ADA assay will be provided.

Summary tables will include all safety events up to 30 days following treatment discontinuation. Listings will include all reported data.

The immunogenicity population will be used for all summaries. The data conversion rules for immunogenicity analysis are listed below:

Operational Data Conversion Table for Immunogenicity Analysis

Assay	Result Type	Result = "Concentration (Titer Units)"	Pos/Neg for Incidence Table	Numerical Value for Display	Numerical Value for Calculation
Anti-BMN111 TAb	Numeric Titer	Negative Screen	Negative	1	0
		Negative Immunodepletion	Negative	1	0
		Negative Titer (≤ 10)	Negative	1	0
		* Value * (e.g. 20, 30, ...)	Positive	e.g. 20, 30, ...	e.g. 20, 30, ...
		Imputed values - none MRD of assay: 10			
Anti-BMN111 NAb	Numeric Titer	Negative Screen	Negative	1	0
		Negative Immunodepletion	Negative	1	0
		Negative Titer (≤ 5)	Negative	1	0
		* Value * (e.g. 10, 20, ...)	Positive	e.g. 10, 20, ...	e.g. 10, 20, ...
		Imputed values – if TAb negative then impute result as 'Negative' for same study visit MRD of Assay: 5			
ANP Reactivity	Binary	Negative Screen	Negative		
		Negative Immunodepletion	Negative		
		Positive Immunodepletion	Positive		
		Imputed values – if TAb negative then impute result as 'Negative' for same study visit			
BNP Reactivity	Binary	Negative Screen	Negative		
		Negative Immunodepletion	Negative		
		Positive Immunodepletion	Positive		
		Imputed values – if TAb negative then impute result as 'Negative' for same study visit			
CNP-22 Reactivity	Binary	Negative Screen	Negative		
		Negative Immunodepletion	Negative		
		Positive Immunodepletion	Positive		

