		Imputed values – if TAb negative then impute result as 'Negative' for same study visit			

The incidence [n(%)] of TAb titer positive results will be summarized for each scheduled visit, and overall (described as ‘Ever Positive’) as follows:

$$\frac{\text{Number of subjects with a positive test result}}{\text{Number of subjects with non – missing TAb result}} * 100$$

The incidence [n(%)] of NAb positive test results, and positive cross-reactivity results for ANP, BNP and CNP, will also be calculated based on the number of subjects with a non-missing TAb result, and summarized at each scheduled visit and overall.

The absolute values (numerical values) of TAb titers and NAb titers will be summarized at Day 1, Week 3, Week 13, Week 26, and Week 52, and presented separately by cohort and overall by treatment group using format as specified in [Table 5.4](#).

The mean (SD) TAb titer, number of hypersensitivity adverse events (HAEs) excluding injection site reactions, and number of subjects experiencing HAE’s will be summarized by the highest HAE CTCAE Grade, and presented by TAb status (negative or positive) and separately by cohort and overall by treatment group using format as specified in [Table 5.4](#).

A line graph of the mean TAb titer (+/- SE) will be presented over time for each visit by pooled placebo, active for each cohort (pooled for sentinel and randomized subjects), and overall. A similar figure will be generated for NAb titers.

The relationship between immunogenicity (ADA status: negative or positive) and measures of safety and efficacy will further be presented graphically by treatment group:

- Box plot of change from baseline at week 52 in standing height/body length Z-Score by TAb status
- Box plot of change from baseline at week 52 in standing height/body length Z-Score by NAb status
- Box plot of change from baseline at week 52 in standing height/body length by TAb status
- Box plot of change from baseline at week 52 in standing height/body length by NAb status
- Box plot of number of hypersensitivity adverse events by TAb status
- Box plot of number of hypersensitivity adverse events (excluding ISRs) by TAb status
- Box plot of number of injection site reaction adverse events by TAb status

- Box plot of maximum duration of injection site reaction adverse event by TAb status, where injection site hemorrhage, injection site hematoma, injection site bruising, and injection site induration will be excluded.

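### Visit windows cut on the full visit list can move a late antibody or serum bone-marker sample to a visit where that assay is not scheduled

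*SAP*

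**What the plan says.** SAP Version 2, Section 5.4, classifies an assessment by the study day on which it was taken. One table serves the whole study: "The analysis windows for assessments in 111-206 are defined in Table 5.4.2". Its construction rule is "The upper bound of each visit window will be target day plus half of the difference between the current target day" and the one that follows, each lower bound being the previous upper bound plus one. For the last visit, "The upper bound of Week 52 will be target day plus 42 days". The stated purpose is "The analysis windows are designated to be consecutive for scheduled visits to accommodate delayed visits due to impact of COVID-19", and the default is "Unless otherwise specified, all analyses are based on derived visits".

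Section 19 says antibody samples are "drawn pre-dose on Day 1, Week 3, Week 13, Week 26, Week 52, and early termination visit", and that "TAb titers and NAb titers will be summarized at Day 1, Week 3, Week 13, Week 26, and Week 52". Antibody incidence is reported for each scheduled visit and overall, as an Ever Positive row. Section 17 says serum collagen X and BSAP "are collected pre-dose at baseline, Day 8, Week 6, Week 20, Week 39, early termination visit", and summarizes them at scheduled visits without naming them. Neither section has its own windows, or a rule for a sample that falls in the window of a visit at which the assay was not due.

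**The concern.** Midpoint windows absorb delay only if the next window belongs to a visit at which the same assay is taken, or if each window runs to the midpoint between that assay's own visits. Neither is true here. Antibodies and serum bone markers skip alternate visits, so the window ends halfway to a visit at which nothing was planned for that assay. A sample later than that midpoint takes the label of the unplanned visit.

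For titers the consequence follows from the text, because Section 19 names a closed list of summary visits and the new label is not on it. For bone markers and antibody incidence, the phrase scheduled visits leaves it open whether the sample appears in a row of its own or not at all. Either way the rule works against its stated aim for these assays. Section 21 plans a summary of visits that were late because of COVID-19, so delays were expected.

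**Working it through.** **Inputs.** Target days from Table 5.4.2: Day 8 and Weeks 3, 6, 13, 20, 26, 39, 52 = 8, 22, 43, 92, 141, 183, 274, 365. Sampling visits from Sections 17 and 19.

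**1. Reproduce the plan's table.** Upper bound = target + (next target − target)/2, half days rounded up:

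- Day 8: 8 + 14/2 = 15
- Week 3: 22 + 21/2 = 32.5 → 33
- Week 6: 43 + 49/2 = 67.5 → 68
- Week 13: 92 + 49/2 = 116.5 → 117
- Week 20: 141 + 42/2 = 162
- Week 26: 183 + 91/2 = 228.5 → 229
- Week 39: 274 + 91/2 = 319.5 → 320
- Week 52: 365 + 42 = 407

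All eight match the SAP. The grid runs from Day 4 to Day 407 without a gap.

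**2. Lateness at which the label changes.** Tolerance = upper bound − target. One day more gives the next label, which lasts until that window ends.

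| Assay, planned visit | Tolerance (days) | Days late when mislabelled | Label received |
|---|---|---|---|
| Antibody Week 3 | 33 − 22 = 11 | 12 to 46 | Week 6 |
| Antibody Week 13 | 117 − 92 = 25 | 26 to 70 | Week 20 |
| Antibody Week 26 | 229 − 183 = 46 | 47 to 137 | Week 39 |
| BSAP/collagen X Day 8 | 15 − 8 = 7 | 8 to 25 | Week 3 |
| BSAP/collagen X Week 6 | 68 − 43 = 25 | 26 to 74 | Week 13 |
| BSAP/collagen X Week 20 | 162 − 141 = 21 | 22 to 88 | Week 26 |
| BSAP/collagen X Week 39 | 320 − 274 = 46 | 47 to 133 | Week 52 |

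No label in the last column is a sampling visit for the assay in its row. The upper ends come from the end of the receiving window, for example 68 − 22 = 46. Still later samples fall in the next sampled window, or, for BSAP/collagen X at Week 39, beyond Day 407.

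**3. Same rule on each assay's own visits.**

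- Antibodies: 22 + 70/2 = 57; 92 + 91/2 = 137.5 → 138; 183 + 182/2 = 274. The windows are Week 3 = Day 4–57, Week 13 = 58–138, Week 26 = 139–274, Week 52 = 275–407.
- BSAP/collagen X: 8 + 35/2 = 25.5 → 26; 43 + 98/2 = 92; 141 + 133/2 = 207.5 → 208. The windows are Day 8 = Day 4–26, Week 6 = 27–92, Week 20 = 93–208, and Week 39 from Day 209. Week 39 is the last scheduled serum sample, so its upper bound must be chosen.

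**4. Weight of one sample.** The planned minimums are 27, 17 and 17 randomized children. A cohort arm therefore has about 17/2 to 27/2 children, roughly 8 to 14, and one absent value is 1/14 = 7% to 1/8 = 13% of a cell. Over all cohorts there are 61 randomized, about 30 per arm, and one value is about 3%.

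**The case against.** A reader might infer that Section 5 itself bars these samples, since it admits to tables only assessments assigned to a visit through the windows. It does not. The grid has no gap between Day 4 and Day 407, so a mislabelled sample is still assigned. Loss follows only where the summary visits are a closed list, and only the titer summary has one. A late BSAP result could properly be printed under Week 26. This stands: for bone markers and antibody incidence the plan is ambiguous between loss and a stray row.

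A reader might also count days. Windows with no antibody visit cover 12 + 35 + 45 + 91 = 183 of the 404 days (45%), and windows with no serum bone-marker visit cover 18 + 49 + 67 + 87 = 221 (55%). These are shares of the calendar and not of samples, which cluster near their target days. They say nothing about how many samples are lost.

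Much antibody reporting does not depend on visit: the Ever Positive row, the box plots by antibody status, and the listings. Nothing in the SAP excludes late samples from Ever Positive, though it does not say that they are included.

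Finally, a common time grid is a defensible choice. Own-schedule windows are much wider: antibody Week 3 grows from 18 to 54 days, Week 26 from 67 to 136, and BSAP Week 20 from 45 to 116. An antibody sample on Day 274 would be shown as Week 26 although it is 274 − 183 = 91 days past target. This also stands, and belongs in the cost of the change.

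**Conclusion.** The point holds in a limited form. For antibody titers, a sample late by at least 12 days (Week 3), 26 days (Week 13) or 47 days (Week 26) gets a label outside the titer visits in Section 19. For serum BSAP and collagen X, the thresholds are 8, 26, 22 and 47 days at Day 8 and Weeks 6, 20 and 39, and the result is either loss from the by-visit table or a stray row. Shorter delays do no harm.

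This assumes that Sections 17 and 19 follow the derived-visit default, since neither states otherwise. The number of samples affected cannot be computed, because the SAP gives no frequency of delay.

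The affected outputs are descriptive secondary tables and plots. It would be wrong to infer a threat to the main result. Growth is measured at both Week 39 and Week 52, so this mechanism does not touch the primary endpoint. It is a cheap improvement to a rule that works against its own purpose for these assays.

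**What to change.** In Section 5.4, define windows per assay from its own sampling visits with the same midpoint rule. For antibodies: Week 3 = Day 4–57, Week 13 = Day 58–138, Week 26 = Day 139–274, Week 52 = Day 275–407. For serum BSAP and collagen X: Day 8 = Day 4–26, Week 6 = Day 27–92, Week 20 = Day 93–208, and Week 39 from Day 209 with a stated upper bound. In Section 19, state that all post-baseline samples count toward Ever Positive, whatever their visit label.

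The cost is one added table and assay-level windows in the programming; no new data are needed. The price in interpretation is that some samples would be tabulated up to about 90 days from target. Section 5.4 already takes the assessment nearest the target when a window holds several, so this concerns only children with no closer sample. A stated maximum distance from target, or a display of actual sampling day beside the by-visit summaries, would limit it further.

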5.5 Handling of Dropouts and Missing Data

For descriptive summaries, missing data will not be imputed. For model-based analyses, an imputation will be conducted for endpoints missed at Week 52. Detailed imputation rules are described in Section 14.1.

Other than for partial/missing dates described below, there will be no imputation for safety data.

5.5.1 Partial Dates

Where start and stop dates for medications or adverse events are incomplete, imputation rules will be applied.

In the event that the start date of a medication/AE is partial, the following imputation rules will be applied:

- If only day is missing, then the start date will be imputed as the first day of the month. If month and year are the same as the month and year of first dose of study treatment, then the start date will be imputed as the first dose date in the study in which the AE occurred.

- If only year is non-missing, then the start date will be imputed as the first day of the year. If year is the same as the year of first dose of study treatment, then the start date will be imputed as the first dose date in the study in which the AE occurred.

In the event that the stop date of a medication/AE is partial, the following imputation rules will be applied:

- If only day is missing, then the end date will be imputed as the last day of the month.
- If only year is non-missing, then the end date will be imputed as the last day of the year. If the imputed date is beyond the study completed or discontinued date of the study in which the AE occurred, the imputed date will be replaced with the study completed or discontinued date.

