11 PRIOR AND CONCOMITANT MEDICATIONS

Prior and concomitant medications will be summarized for the FAS. For analysis purposes, the following definitions will be used to determine prior and concomitant medications for the entire study period:

- Prior medications: Any medications taken and ended prior to the initial study treatment administration date will be considered prior medications.
- Concomitant medications: Any medications taken on or after the initial study treatment administration date up to 30 days after discontinuation of study treatment will be considered concomitant medications and included in summary tables. This also includes medications initially taken prior to the initial study treatment administration date but continued or ended on or after the initial study treatment administration date.

Concomitant medications will be summarized separately by cohort and overall by treatment group using format as specified in [Table 5.4](#), and a separate summary will be provided which includes only those concomitant medications that were initiated on study.

All medications will be coded using the latest version available within BioMarin of the World Health Organization Drug (WHO Drug) dictionary (Version September 2021). Prior and concomitant medication use will be separately summarized by Anatomical Therapeutic Chemical (ATC) medication class (Level 2) and preferred name (i.e., generic medication name). If a medication doesn't have ATC level 2, they are grouped as "ATC Level 2 classification unavailable". A subject reporting the same medication more than once will be counted once when calculating the number and percentage of subjects who received that medication. A listing of prior and concomitant medications will be provided. In addition, a listing for COVID vaccine will be provided.

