15.1 Adverse Events

Adverse events (AEs) will be coded in accordance with MedDRA Version 24.1 and performed prior to DBL. Coding of the severity of AEs is performed by the investigators using national cancer institute (NCI) CTCAE version 4.03, where events are coded from CTCAE Grade 1 to Grade 5.

Only TEAEs defined as any adverse event that newly appeared, increased in frequency, or worsened in severity following initiation of study treatment administration are reported by the investigators and consequently are included in the summary tables.

In the event that the start date of an AE is incomplete or missing, conservative imputation rules are applied so that where there is uncertainty, the event is considered treatment emergent. Similarly, the AE end dates are imputed in a conservative manner to a maximum length.

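### Section 5.5.1 moves partial start dates to the first dose date without checking the stop date, so a start can fall after its stop; separately, medications begun before dosing can be counted as started on study

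*SAP*

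**What the plan says.** All references are to SAP Version 2 (02 February 2022).

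- **Scope, Section 5.5.1.** One rule serves both kinds of record: "In the event that the start date of a medication/AE is partial, the following imputation rules will be applied".
- **Day missing.** The default is the first of the month. A match with the month of first dose is an exception, and Day 1 is used instead: "If month and year are the same as the month and year of first dose of study treatment, then the start date will be imputed".
- **Only the year known.** The default is the first day of the year, again with an exception, under which "then the start date will be imputed as the first dose date". The trigger for that exception is a matching calendar year: "If year is the same as the year of first dose of study treatment".
- **The only bound in the section** concerns stop dates. It replaces an imputed stop date with the completion or discontinuation date: "If the imputed date is beyond the study completed or discontinued date of the study in which the AE occurred". Nothing requires the start to be on or before the stop.
- **Purpose, Section 15.1.** Imputation of adverse event start dates is meant to be conservative, so that "where there is uncertainty, the event is considered treatment emergent". The paragraph before it says that investigators report only treatment-emergent events.
- **Medications, Section 11.** A medication is prior if it ended before first dose. Those taken on or after first dose, including ones begun earlier and continued, are concomitant. A further summary "includes only those concomitant medications that were initiated on study".

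**The concern.** There are two separate mechanisms.

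First, the rule is silent on the stop date. When the stop is known to precede first dose, moving the start to the first dose date gives a record that begins after it ends. For an adverse event, this also settles as treatment-emergent a case in which nothing was uncertain. Section 15.1.2 plans event duration and time from first dose to first onset for injection site reactions, hypotension and heart rate changes. Both use these dates.

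Second, a rule built to be cautious for adverse events is applied unchanged to medications. There, moving a start forward to Day 1 is not cautious. It turns a medication the child may already have been taking into one that appears to have been started on study.

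The year-only condition is easily met in the youngest children. Section 4.2 has Cohort 3 begin treatment before 6 months of age. With a first dose from July onward, the infant's whole pre-dose life lies in the calendar year of first dose.

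**Working it through.** The plan gives no figure to reproduce. The check applies the Section 5.5.1 rule literally to example records. The dates are invented, with an assumed first dose on 20 June 2020.

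**Worked cases**

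| Record | Start under 5.5.1 | Stop minus start | Result |
|---|---|---|---|
| (a) AE, start June 2020, stop 10 June 2020 | 20 June | 10 − 20 = −10 days | Start after stop; treatment-emergent by date |
| (b) AE, start 2020, stop 15 February 2020 | 20 June | −(14 + 31 + 30 + 31 + 20) = −126 days | Same |
| (c) AE, start 2020, stop May 2020 (imputed as 31 May) | 20 June | −20 days | The section's own start and stop rules conflict |
| (d) Medication, start June 2020, stop 5 June 2020 | 20 June | 5 − 20 = −15 days | Prior under Section 11 by its stop date, yet start is on Day 1 |
| (e) Medication, start 2020, ongoing | 20 June | not defined | Concomitant, and started on study by date |
| (f) AE, start June 2020, ongoing | 20 June | not defined | Treatment-emergent, as Section 15.1 intends |

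**Is (c) really free of uncertainty?** Yes. Section 5.5.1 imputes a partial stop as the last day of the known month or year, the latest day the record allows. If even that day precedes first dose, the event was over before dosing.

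**All cases in the month of first dose.** There are 19 days before 20 June. The possible pairs of true start and stop with start ≤ stop < first dose number 19 × 20 / 2 = 190. With the start day missing and the stop day known, the literal rule gives a start after the stop, and treatment-emergent by date, in 190 of 190. With a guard (if the stop precedes first dose, use the first day of the known month or year) the count is 0 of 190.

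**What the guard leaves alone.** Case (f) is unchanged, as it should be. Case (e) is also unchanged, so the medication problem needs its own rule.

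**Largest displacement of a true start.** With the day missing, 31 − 1 = 30 days. With only the year known, 365 − 1 = 364 days in a non-leap year.

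**The case against.** The best case against the point is that other sections block most of the harm. Three stronger readings are tempting, and the document does not support them.

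- **That the tables of treatment-emergent events are inflated with pre-dose events.** Section 15.1 says investigators report only treatment-emergent events, so an event that ended before first dose should not be in the adverse event data. The 190 of 190 describes the rule, not records the plan expects to exist. What stands is that any such record that does reach the database would be handled wrongly.
- **That medications stopped before dosing enter the started-on-study table.** They cannot. Section 11 classes them as prior by their end date, and the table draws only on concomitant medications. What stands is the date conflict in (d) and the separate problem in (e), which does not depend on an early stop.
- **That about half of year-only starts in the year of first dose are misdated.** Such a figure follows from assuming onset spread evenly over the year, but it is not conditioned on a stop before first dose. It mostly covers records where setting Day 1 is ordinary conservative practice for adverse events. Even spread also sits badly with the reporting of treatment-emergent events only. The Cohort 3 observation shows that the calendar condition can be met, not that infants' records have year-only starts.

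It can also be argued that Section 15.1 already limits the rule to uncertain cases. It states that principle, but Section 5.5.1 gives an explicit instruction without the limit. For (a) to (c) a programmer cannot follow both.

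**Conclusion.** The point holds as a minor defect. As written, Section 5.5.1 produces a start after the stop for every record that has a partial start in the month or year of first dose and a complete or imputed stop before first dose. For adverse events this goes beyond the principle in Section 15.1, though few such events are expected. For medications that ended before first dose it gives conflicting dates without changing their classification. Medications begun earlier in the same month or year and continued past first dose can be counted as started on study.

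The number of records affected cannot be estimated, because the SAP gives no count of partial dates. Only descriptive safety and medication outputs could change; the primary and key secondary efficacy analyses do not use these dates. The conclusion assumes that the rule is programmed literally and that treatment-emergent and started-on-study status are read from the imputed start. Dating an adverse event to first dose when its stop is missing, ongoing, or on or after first dose is not criticised.

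**What to change.** Two additions to the SAP:

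1. **Section 5.5.1.** Impute the start as the first dose date only when the stop date is missing, ongoing, or on or after first dose. If the complete or imputed stop date is before first dose, impute the start as the first day of the known month or year.
2. **Section 11.** Do not count a medication as started on study on an imputed start date alone when the collected data show use before first dose.

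The first costs one sentence and one programming condition. It leaves the conservative default in place for every other event. The second also needs little text, but its programming depends on what the case report form records about medication use before dosing. The SAP does not describe such a field, so this should be checked before the rule is fixed.
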